13.0 Study Timelines*

13.1 Describe the anticipated duration needed to enroll all study subjects.

Response:

2 to 4 months

13.2 Describe the duration of an individual subject's participation in the study. Include length of study visits, and overall study follow-up time.

Response: An individual subject will complete the study in about 42 days, from screening and enrollment at day -1 or 1 to follow-up on day 42 ± 3 days. After enrollment, there are a total of 5 telemedicine study visits. Each will last approximately 15-30 minutes.

13.3 Describe the estimated duration for the investigators to complete this study (i.e. all data is collected and all analyses have been completed).

Response:

Up to 6 months

14.0 Setting

14.1 Describe all facilities/sites where you will be conducting research procedures. Include a description of the security and privacy of the facilities (e.g. locked facility, limited access, privacy barriers). Facility, department, and type of room are relevant. Do not abbreviate facility names.

NOTE: Examples of acceptable response may be: "A classroom setting in the Department of Psychology equipped with a computer with relevant survey administration software," "The angiogram suite at Buffalo General Medical Center, a fully accredited tertiary care institution within New York State with badge access," or, "Community Center meeting hall."

Response: Because of the highly contagious nature of COVID infection in the first few days after onset of symptoms, it is essential to minimize exposure of research team members to the subjects. Therefore, except for the enrollment visit, all procedures for this study will be conducted remotely at the subject's home. The interviewer will maintain privacy and security by ensuring their conversation cannot be overhead and that all study related documents are stored in a password protected folder with access limited to study personnel. The IP and matching placebo will be stored and distributed from the Research Pharmacy at the CRC. Study packages that contain daily symptom questionnaire, daily temperature and pulse oximetry logs, a thermometer, a pulse oximeter, saliva collection kits and return packaging will be assembled in the CRC by the research coordinator and be given to subject at the time of consent. We anticipate 2 courier visits to the participant's homes. On Day 15-17 to pick up saliva samples and questionnaires and unused IP and then on Day 29-31 to pick up the last saliva sample and unused study materials.

14.2 For research conducted outside of UB and its affiliates, describe:

- *Site-specific regulations or customs affecting the research*
- *Local scientific and ethical review structure*

NOTE: This question is referring to UB affiliated research taking place outside UB, i.e. research conducted in the community, school-based research, international research, etc. It is not referring to multi-site research. UB affiliated institutions include Kaleida Health, ECMC, and Roswell Park Cancer Institute.

Response: NA

N/A: This study is not conducted outside of UB or its affiliates.

15.0 Community-Based Participatory Research

15.1 *Describe involvement of the community in the design and conduct of the research.*

NOTE: Community-Based Participatory Research (CBPR) is a collaborative approach to research that equitably involves all partners in the research process and recognizes the unique strengths that each brings. CBPR begins with a research topic of importance to the community, has the aim of combining knowledge with action and achieving social change to improve health outcomes and eliminate health disparities.

Response: NA

N/A: This study does not utilize CBPR.

15.2 *Describe the composition and involvement of a community advisory board.*

Response: NA

N/A: This study does not have a community advisory board.


Describe other resources available to conduct the research.

16.2 Describe the time and effort that the Principal Investigator and research staff will devote to conducting and completing the research.

NOTE: Examples include the percentage of Full Time Equivalents (FTE), hours per week. The question will elicit whether there are appropriate resources to conduct the research.

Response:

[name] 0.05 FTE

[name] 0.05 FTE

[name] 0.05 FTE

[name] 0.05 FTE

[name] 0.05 FTE

16.3 Describe the availability of medical or psychological resources that subjects might need as a result of anticipated consequences of the human research, if applicable.

NOTE: One example includes: on-call availability of a counselor or psychologist for a study that screens subjects for depression.

Response: If a research staff determines that the participant needs additional medical or psychological resources during the course of the study, they will ask the participant to contact their primary care practitioner in non-emergent situation or to go the Emergency Department in emergent situations.

16.4 Describe your process to ensure that all persons assisting with the research are adequately informed about the protocol, the research procedures, and their duties and functions.

Response: The co-PIs of this study will assign the research team members the research related duties and ensure that they are adequately trained to perform the duties. Any amendments to the study protocol and any events that alter the risk-benefit ratio of the study will be promptly communicated to the team members.

17.0 Other Approvals

17.1 Describe any approvals that will be obtained prior to commencing the research (e.g., school, external site, funding agency, laboratory, radiation safety, or biosafety).

Response:

N/A: This study does not require any other approvals.

18.0 Provisions to Protect the Privacy Interests of Subjects

18.1 Describe how you will protect subjects' privacy interests during the course of this research.

NOTE: Privacy refers to an individual's right to control access to him or herself. Privacy applies to the person. Confidentiality refers to how data collected about individuals for the research will be protected by the researcher from release. Confidentiality applies to the data.

Examples of appropriate responses include: "participant only meets with a study coordinator in a classroom setting where no one can overhear", or "the participant is reminded that they are free to refuse to answer any questions that they do not feel comfortable answering."

Response:

Prospective subjects will be interviewed over the phone where the interviewer will be in a private room. Subjects will be at their residence or place of work.

18.2 *Indicate how the research team is permitted to access any sources of information about the subjects.*

*NOTE: Examples of appropriate responses include: school permission for review of records, consent of the subject, HIPAA waiver. This question **does apply** to records reviews.*

Response: HIPAA waiver. Consent of the participants.

19.0 Data Management and Analysis*

19.1 *Describe the data analysis plan, including any statistical procedures. This section applies to both quantitative and qualitative analysis.*

Response:

Randomization: Participants will be randomized to the intervention or control arm in a 2:1 fashion using a permuted block randomization scheme. The randomization lists to be used in this study will be generated by the study biostatistician. Subjects will be included in data analyses according to their randomized assignment irrespective of the treatment actually received (intent-to-treat).

Missing data: The amount and nature of missing data will be characterized and no method of imputation will be used for missing data. We acknowledge the possibility of informative missingness with some of the outcomes, that is, the probability of a particular observation being missing may be related to the health or death of a subject, and therefore analyses will be interpreted with caution.

Accrual: Participants will be accrued to the study on a first-come basis. The projected accrual is approximately 15 per month, and therefore recruitment is expected to be complete at most 60 days following the study starting point. Subjects will be followed for 1 month after recruitment completion, so total study duration will be approximately 3 months. During the enrollment period, the study biostatistician will model and predict accrual rates in order to verify adequacy of the enrollment process.

Descriptive analyses: Measured outcome variables will be summarized overall and by relevant demographic and baseline variables. Descriptive statistics such as frequencies and relative frequencies will be computed for all categorical variables. Numeric variables will be summarized using simple descriptive statistics such as the mean, standard deviation and range. A variety of graphical techniques will also be used to display data, ex., histograms, boxplots, scatterplots, etc.

Statistical analyses: Analyses will be performed with a focus on estimation of specific clinically important parameters, including preliminary evidence of safety and activity of the intervention, for use in the planning of subsequent comparative trials designed to fully assess safety and efficacy. The primary outcomes in the examination of the study intervention, specifically, the cumulative incidence of serious adverse events (SAEs), the cumulative incidence of Grade 3 and 4 adverse events (AEs), and the discontinuation or temporary suspension of the investigational medication (for any reason), are measured in a binary fashion at the

study participant-level. The corresponding probabilities will each be estimated using the relative frequency. In addition to the point estimates based on collected data, 95% confidence intervals will also be computed based on the methodology of Clopper and Pearson. Additional binary study outcomes, ex., incidence of COVID-related hospitalization and hospitalization for any reason, will be analyzed in an identical fashion. Comparison between randomized groups with regards to these outcomes will be done using Fisher's exact test. For numeric outcomes, such as symptom questionnaire results and measures of clinical improvement, the rank-based Wilcoxon rank sum test will be used to compare groups. For outcomes which may be subject to censoring such as speed of resolution of COVID related symptoms, parameter estimation will be based on the Kaplan-Meier estimator and the log-rank test will be utilized to compare groups. Proposed exploratory outcomes are collected longitudinally. Proposed exploratory outcomes are collected longitudinally. Standard statistical techniques for the analysis of such outcomes, ex., mixed linear models, will be utilized. Although primary analyses will be performed based on the intent-to-treat principle, to evaluate the robustness of these results, analyses will also be conducted in a secondary fashion based on actual treatment received. All statistical tests will be two-sided and tested at a 0.05 nominal significance level. All analyses will be carried out using SAS version 9.4 (or higher) statistical software (Cary, NC).

19.2 *If applicable, provide a power analysis.*

NOTE: This may not apply to certain types of studies, including chart/records reviews, survey studies, or observational studies. This question is asked to elicit whether the investigator has an adequate sample size to achieve the study objectives and justify a conclusion.

Response:

Sample size justification: In that accurate assessment of the safety of the study intervention is of utmost importance in this study, the sample size of 20 in the intervention group is based on the expected precision associated with our estimated safety probabilities corresponding to the primary outcomes expressed in terms of confidence interval width. Note that a true probability of 0.5 represents the mathematically worst-case scenario with regards to precision and therefore we may take precision at that point to be an upper bound of expected accuracy. We see that with a sample size of 20 participants the standard error of these estimators will be at most 11 percentage points.

19.3 *Describe any procedures that will be used for quality control of collected data.*

Response: Collected data will be reviewed by the co-PIs on a weekly basis to ensure adequate data collection.

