- Take the IP 3 times a day orally for 14 days.
- On Days 3, 7, 14, 28 and 42 collect a sample of saliva prior to taking drug in a collection container provided. Place the sample in a collection bag and place it in a freezer.
- Speak to the research coordinator through telemedicine on Days 3, 7, 14, 28 and 42 to provide

data as well as any adverse effects of the treatment. These include anxiety and depression and drowsiness special interest adverse events. The duration of these visits will be 15-30 minutes.

- Allow a courier to come to your house to collect study related materials on Day 15 ± 3 and day 43 ± 3 to pick up study related materials.

12.2 Describe what data will be collected.

NOTE: For studies with multiple data collection points or long-term follow up, consider the addition of a schedule or table in your response.

Response: Please see Table above

12.3 List any instruments or measurement tools used to collect data (e.g. questionnaire, interview guide, validated instrument, data collection form).

Include copies of these documents with your submission.

Response: Included documents: 1) Data collection form (baseline); 2) Data collection form (Follow-up); 3) Daily symptom questionnaire; 4) Body temperature and pulse oximetry logs; 5) Instructions for saliva collection, storage and shipping 6) WHO Clinical Progression Scale

12.4 Describe any source records that will be used to collect data about subjects (e.g. school records, electronic medical records).

Response: EMR data will be accessed to ascertain baseline health information and information relevant to the participants COVID illness. The study team will have remote access to the relevant EMRs.

12.5 Indicate whether or not **individual** subject results, such as results of investigational diagnostic tests, genetic tests, or incidental findings will be shared with subjects or others (e.g., the subject's primary care physician) and if so, describe how these will be shared.

Response: No

12.6 Indicate whether or not **study** results will be shared with subjects or others, and if so, describe how these will be shared.

Response: Study results will be posted on Clinical Trials.gov and submitted for publication in a peer reviewed journal.

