21.0 Provisions to Monitor the Data to Ensure the Safety of Subjects*

N/A: This study is not enrolling subjects, or is limited to records review procedures only. This section does not apply.

NOTE: Minimal risk studies may be required to monitor subject safety if the research procedures include procedures that present unique risks to subjects that require monitoring. Some examples include: exercising to exertion, or instruments that elicit suicidality or substance abuse behavior. In such cases, N/A is not an acceptable response.

21.1 Describe the plan to periodically evaluate the data collected regarding both harms and benefits to determine whether subjects remain safe.

Response: On a weekly basis the co-PIs will review the data being collected to determine if there are any worrisome patterns of the adverse events (grade 3 or 4) and SAEs reported. This review will be blinded. We do anticipate a 20% rate of hospitalization in our subjects. Therefore, only if the rate is much higher than that will there be a cause of concern.

21.2 Describe what data are reviewed, including safety data, untoward events, and efficacy data.

Response: All safety data will be reviewed.

External Review of Data

[name], an infectious disease specialist at University of Buffalo will serve as an external reviewer for the outcomes collected in this study. Specifically, he will adjudicate whether the adverse events (grade 3 or 4) and SAEs collected are drug or disease related. He will also adjudicate whether the hospitalizations observed in this study were COVID related or not. These adjudications will be on blinded data.

21.3 Describe any safety endpoints.

- Response: Cumulative incidence of serious adverse events (SAEs)
 - Cumulative incidence of Grade 3 and 4 adverse events (AEs).
 - Adverse effects of special interest: Anxiety and Depression (GAD-2 and PHQ-2 questionnaires); Drowsiness (will be recorded)
 - Discontinuation or temporary suspension of the investigational medication (for any reason).

21.4 Describe how the safety information will be collected (e.g., with case report forms, at study visits, by telephone calls with participants).

Response: The safety information will be collected by scheduled phone calls as described above.

21.5 Describe the frequency of safety data collection.

Response: Days 1, 3, 7, 14, 28 and 42

21.6 Describe who will review the safety data.

Response: The co-PIs will review the data along with the biostatistician [name].

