23.0 Risks to Subjects*

23.1 List the reasonably foreseeable risks, discomforts, hazards, or inconveniences to the subjects related to their participation in the research. Consider physical, psychological, social, legal, and economic risks. Include a description of the probability, magnitude, duration, and reversibility of the risks.

NOTE: Breach of confidentiality is always a risk for identifiable subject data.

Response:

Nasopharyngeal swabs are associated with discomfort that is usually short-lived.

Potential risks associated with the use of planned doses of melatonin include dizziness, headache, vivid dreams, nausea and sleepiness, that are anticipated to be of mild severity.

Breach of confidentiality is an associated risk of this research.

23.2 Describe procedures performed to lessen the probability or magnitude of risks, including procedures being performed to monitor subjects for safety.

Response: The frequent telephonic follow-up and the availability of the study team to the participants in case adverse effects arise.

Please see section 20.1 for procedures performed to lessen the risk of breach of confidentiality.

23.3 If applicable, indicate which procedures may have risks to the subjects that are currently unforeseeable.

Response: Melatonin has never been studied in COVID patients, therefore there are unforeseeable risks.

23.4 If applicable, indicate which research procedures may have risks to an embryo or fetus should the subject be or become pregnant.

Response: Melatonin has not been studied in pregnancy.

23.5 If applicable, describe risks to others who are not subjects.

Response: NA

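### Four of the five melatonin effects the protocol expects, all mild, enter no safety endpoint as events, and drowsiness has no stated analysis

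*Combined protocol and SAP*

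**What the plan says.** Sections 1.0, 3.0 and 21.3 list four safety components: SAEs, Grade 3-4 AEs, special-interest events, and discontinuation or suspension. Section 21.3 defines the third: "Adverse effects of special interest: Anxiety and Depression (GAD-2 and PHQ-2 questionnaires); Drowsiness (will be recorded").

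Section 19.1 names three primary outcomes, each binary per participant: any stopping or pausing of drug, whatever the cause, plus "the cumulative incidence of serious adverse events (SAEs), the cumulative incidence of Grade 3 and 4 adverse events (AEs"). It gives each a relative frequency with a Clopper-Pearson interval, and Fisher's exact test between arms. The special-interest events are not mentioned there.

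Section 23.1 says that the risks of melatonin at the planned doses "include dizziness, headache, vivid dreams, nausea and sleepiness, that are anticipated to be of mild severity".

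Collection has no grade threshold. At the telemedicine visits in section 12.1, subjects report "data as well as any adverse effects of the treatment", and section 21.5 schedules safety data on Days 1, 3, 7, 14, 28 and 42. Under 12.1, subjects also rate COVID symptoms before the first dose and then every evening to Day 42. The symptom list in section 3.0 includes headache, nausea and dizziness.

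For monitoring, the weekly review in section 21.1 looks for "worrisome patterns of the adverse events (grade 3 or 4) and SAEs reported". Section 21.2 limits adjudication of relatedness to the same classes of event, but also states that the whole of the safety data is reviewed. The suspension trigger in 21.9 refers to adverse events possibly due to melatonin, without a grade.

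**The concern.** The severity filter on the safety endpoints does not fit the harms that the protocol itself predicts. If melatonin behaves as section 23.1 expects, its effects will be mild, and the main safety counts are built to exclude mild events. The pilot could then report a clean primary safety result while common low-grade effects appear in no safety table.

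This matters because section 19.1 says the estimates are meant for planning later comparative trials, and section 19.2 makes accurate safety assessment the basis of the sample size. For a capsule taken three times a day for 14 days, low-grade tolerability is an obvious planning input. Common effects are also what a 20-subject arm is best able to see.

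**Working it through.** **The plan's own figure.** Section 19.2 gives a standard error of at most 11 percentage points with 20 subjects. At p = 0.5, sqrt(0.5 × 0.5 / 20) = 0.1118, or 11.2 points, which agrees after rounding. The point below does not change it.

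**Matching expected effects to endpoints.** The effects come from 23.1, the safety components from 1.0, 3.0 and 21.3, and the symptom list from 3.0. Severity is taken as mild, as 23.1 expects.

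| Effect in 23.1 | SAE or Grade 3-4 if mild | Special-interest event | COVID symptom list |
|---|---|---|---|
| Dizziness | No | No | Yes |
| Headache | No | No | Yes |
| Vivid dreams | No | No | No |
| Nausea | No | No | Yes |
| Sleepiness | No | Yes, as drowsiness | No |

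One of five matches a safety component and four do not. (A mild event would not ordinarily be serious.) A mild case of any of the four reaches the safety result only by stopping or pausing drug, and then it counts as a discontinuation, not as the event. Section 19.1 leaves out the special-interest events, so the one match, drowsiness, has no stated analysis either.

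**How much could go uncounted.** Arm sizes under 2:1 allocation of 30 are 30 × 2/3 = 20 and 30 × 1/3 = 10. The documents give no rate for mild effects, so the rates below are assumptions. Expected count = 20p; chance of at least one = 1 − (1 − p)^20.

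| Assumed true risk on melatonin | Expected of 20 | Chance of at least one |
|---|---|---|
| 5% | 1 | 64% |
| 10% | 2 | 88% |
| 20% | 4 | 98.8% |
| 30% | 6 | 99.9% |

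None of these events would add to the Grade 3-4 count.

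**What an any-grade table would show.** The 95% Clopper-Pearson intervals are 0 to 16.8% for 0/20, 1.2 to 31.7% for 2/20, 5.7 to 43.7% for 4/20, and 0 to 30.8% for 0/10 on placebo. These are wide but usable for planning.

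**What it would not show.** Fisher's exact test, 20 against 10, two-sided 0.05, has power of about 10% for assumed risks of 30% against 10%, and about 12% for 50% against 30%. With 0/10 on placebo, 7/20 on melatonin gives p = 0.064 and 8/20 gives p = 0.029. The table would support estimates, not tests.

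**The case against.** The strongest reply is that little information is lost. Any-grade events are already asked about at each visit. Section 19.1 promises frequencies for all categorical variables and leaves its list of further binary outcomes open, so an any-grade table would fit the plan. Headache, nausea and dizziness are rated daily, and 19.1 compares questionnaire results between arms.

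Much of this stands. The gap is in endpoints and analysis, not in collection. A reader might infer that these effects are never compared with placebo. The documents do not support that for headache, nausea and dizziness. Those three, however, are compared as efficacy outcomes, so a headache caused by the drug would look like slower COVID recovery. The general descriptive text does not close the gap: it covers outcome variables, overall and by demographic and baseline variables. Grade 1-2 events are not a listed outcome, and arm is not named there.

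A reader might also infer that all safety monitoring ignores low grades. That is too strong as well, given the unrestricted statement in 21.2 and the ungraded trigger in 21.9. What remains is that 21.1 is narrower than both.

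Third, separating drug effect from disease is hard. Subjects enrol within 5 days of symptom onset, when symptoms may worsen naturally, and there are about 10 placebo subjects. This limits what the added table can prove, but not the case for tabulating the events.

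**Conclusion.** The point holds as a gap in endpoints and analysis. At the severity the protocol expects, four of its five named melatonin effects enter no safety endpoint as events, and the fifth is listed as a special-interest event but has no analysis in 19.1. Vivid dreams alone appears on no list in the documents.

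The count of four in five rests on reading sleepiness as drowsiness and on the effects being mild; a Grade 3-4 or serious case of any of them would be counted. The illustration of 4 or 6 subjects in 20 rests on assumed risks of 20% or 30%. It should not be read as predicting that the Grade 3-4 endpoint will be 0/20: section 21.1 anticipates 20% hospitalization, so COVID itself may produce severe events.

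The change is worth making because safety is the primary objective and the adverse event data are already gathered. No sample size or existing endpoint needs to change.

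**What to change.** 1. In 3.0, 19.1 and 21.3, add the by-arm incidence of adverse events of any grade (any event, and each of the five effects in 23.1) and of the special-interest events. Use the Clopper-Pearson intervals already planned, and state that they are read as estimates, not tests.
2. For headache, nausea and dizziness, also report onset or worsening from the pre-dose Day 1 rating. Note that early COVID can worsen naturally and that about 10 placebo subjects give only a rough comparison.
3. Ask about vivid dreams at the existing visits or in the evening questionnaire, and about drowsiness if it is not already on the form. The forms are separate attachments and were not available for this review.
4. Reconcile the scope of review in 21.1 with the statement in 21.2 and the ungraded trigger in 21.9.

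The cost is one extra table, one or two questionnaire items and a short amendment. The downside is that some counted events will be COVID symptoms, which the placebo arm and the Day 1 comparison separate only in part.
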